8. SELECTION AND WITHDRAWAL OF SUBJECTS

8.1. Subject Inclusion Criteria

Subjects must fulfill all of the following inclusion criteria to be eligible for participation in the study.

1. Capable of giving written informed consent and able to effectively communicate with the investigator and study personnel. A signed ICF must be on file prior to initiating the Screening procedures;
2. Willing and able to complete all study requirements, restrictions, visits and procedures;

3. [REDACTED]

- [REDACTED]
5. Male or female between 18 and 75 years of age (inclusive);
 6. Females of reproductive potential, defined as women who have not been postmenopausal for at least 24 consecutive months (i.e., who have had menses within the preceding 24 months), or women who have not undergone surgical sterilization; specifically, hysterectomy, bilateral salpingectomy, bilateral oophorectomy, hysteroscopic sterilization, and/or tubal ligation, must have a negative pregnancy test at Screening and within the 24-hour period prior to Day 1;
 7. All participants must agree not to participate in a conception process (i.e., active attempt to become pregnant or to impregnate, sperm or egg donation, in vitro fertilization). If participating in sexual activity that could lead to pregnancy, the participant must agree to use 2 reliable methods of contraception simultaneously while receiving study treatment and for 3 months after subject has stopped taking study drug. A combination of TWO of the following methods MUST be used appropriately:
 - a. Condoms (male or female) with or without a spermicidal agent;
 - b. Diaphragm or cervical cap with spermicide;
 - c. IUD;
 - d. Hormonal-based contraception.

Note: Participants who are not of reproductive potential (women who have been postmenopausal for at least 24 consecutive months or have undergone hysterectomy, bilateral salpingectomy, bilateral oophorectomy, hysteroscopic sterilization, and/or tubal ligation, or men who have documented azoospermia) are eligible without requiring the use of contraceptives. Acceptable documentation of sterilization, menopause or male partner's azoospermia must be provided; serum follicle stimulating hormone (FSH) measurement can be used to document menopausal status.

8.2. Subject Exclusion Criteria

Subjects who meet the following criteria prior to the first dose of study drug are not eligible for randomization.

1. Pregnant or breastfeeding or planning to become pregnant during the study period;
2. Known allergy to CRV431, cyclosporine, or any of their inactive ingredients;
3. Positive test for HBsAg, HCVAb or HIVAb. If HCVAb test is positive, then an HCV-RNA test will be performed. If the HCV-RNA test is negative, the subject is allowed to participate in the study, as long as the subject meets all other inclusion criteria and has never been treated for HCV or was treated >2years ago and achieved a sustained virologic response at that time;
4. History of or any current medical condition which could compromise the safety of the participant in the study, as determined by the investigator;
5. Subjects with a systolic pressure >150 or a diastolic pressure >90. At the discretion of the investigator, the blood pressure may be re-measured after 10 minutes to ensure the blood pressure is in fact out of range. Out of range blood pressure after the second measurement will exclude a subject. If a subject has a blood pressure within the desired range due to anti-hypertension medication, that subject can be included at the discretion of the investigator, provided the anti-hypertension medication is not a contraindicated medication. Please refer to [Appendix A](#) for a list of drugs considered contraindicated;
6. Clinically significant gastrointestinal, cardiovascular, neurologic, psychiatric, metabolic, renal, hepatic, respiratory, inflammatory, or infectious disease, as determined by the investigator;
7. Subjects with a history of clinically significant acute cardiac event within 6 months prior to Screening such as stroke, transient ischemic attack, or coronary heart disease (angina pectoris requiring therapy, myocardial infarction, revascularization procedures, with LVEF <50% as determined by previous echocardiography or MUGA scan);
8. Subjects with uncontrolled or unstable cardiac arrhythmias:
 - a. Severe conduction disturbance (e.g., second- or third-degree AV block);
 - b. QTc interval >450 msec (males) or >470 msec (females);
 - c. History of congenital long QT syndrome, congenital short QT syndrome, Torsades de Pointes, or Wolff Parkinson White syndrome;
9. Subjects with transaminases >5 x ULN and with ALP >2 x ULN;
10. Subjects with total serum bilirubin >1.5 x ULN, unless the subject has Gilbert's Syndrome, in which case the subject can be enrolled provided the direct bilirubin is within 30% of the TBL;
11. Subjects with a platelet count <150,000/m³;
12. Systemic immunosuppression within 6 months prior to the first dose of study drug apart from short-term treatment for asthma, COPD or other respiratory conditions;

13. Current clinically significant diarrhea or gastric stasis that, in the investigator's opinion, could influence drug absorption or bioavailability;
14. Subject with any history or presence of decompensated cirrhosis;
15. Other well documented causes of chronic liver disease according to standard diagnostic procedures including, but not restricted to:
 - a. Suspicion of drug-induced liver disease;
 - b. Alcoholic liver disease;
 - c. Autoimmune hepatitis;
 - d. Wilson's disease;
 - e. Primary biliary cholangitis, primary sclerosing cholangitis;
 - f. Genetic hemochromatosis (Homozygosity for C282Y or C282Y/H63D compound heterozygote);
 - g. Known or suspected HCC;
 - h. History or planned liver transplant, or current MELD score >15;
16. History of, or current evidence of, gallstones, gall bladder disease, cholestasis that has not been treated with cholecystectomy, or pancreatitis;
17. Subjects with HbA1c >9.5%. For subjects with an HbA1c >9.5% at the Screening Visit, a repeat test may be performed. A repeat HbA1c result >9.5% will lead to exclusion;
18. At Screening, an eGFR <60 mL/min/1.73 m² (calculated by the CKD-EPI method) and/or a KDIGO category of >G2;
19. Safety laboratory abnormalities at Screening which are clinically significant as determined by the investigator;
20. Weight loss of more than 5% within 3 months prior to randomization;
21. Current abuse of alcohol or illicit drugs, or history of alcohol or illicit drug abuse within the preceding 2 years, as determined by the investigator. History of excess alcohol intake as defined by ≥ 21 units of alcohol per week in males and ≥ 14 units of alcohol per week in females for 2 years prior to enrollment where a "unit" of alcohol is equivalent to 12-ounce beer, 4-ounce of wine, or 1-ounce shot of hard liquor;
22. A positive urine drug screen for drugs with a high potential for abuse (amphetamines, cannabinoids, opiates, cocaine, benzodiazepine) or alcohol test at Screening or Day -1. For benzodiazepine's only: positive results will be accepted if due to an approved prescription. For cannabinoids, opiates and cocaine: On a case by case basis, positive results will be evaluated by the Sponsor and Medical Monitor in order to determine the subject's eligibility to safely be included in the study;
23. Significant medical or psychiatric illness that would interfere with compliance and ability to tolerate treatment as outlined in the protocol;
24. Subjects who cannot be contacted in case of emergency;
25. Judgement by the investigator that the subject should not participate in the study if the subject is unlikely to comply with all study procedures and treatment;

26. Received an investigational drug or investigational vaccine or used an investigational medical device within 30 days prior to first dose of study drug;
27. Subjects who have used any drugs or substances known to be strong inhibitors or inducers of CYP3A4/5 and drugs whose major elimination pathway is the BSEP or OAT3, and drugs that are major substrates of the hepatic uptake transporters, OATP1B1 and OATP1B3 within 30 days prior to the first dose of study drug. (**NOTE:** Please refer to [Appendix A](#) for a list of drugs considered contraindicated. If there are questions, please contact the Sponsor);
28. Subjects with a history of organ transplantation. Corneal transplantation will be allowed.

Abnormal ECG or laboratory parameters may be repeated once, if in the opinion of the investigator, the results are due to technical factors or are inconsistent with the potential subject's medical evaluation.

Potential study subjects who met all inclusion and exclusion criteria for this study but who, for personal or administrative reasons, were not included in a study cohort may be re-screened if more than 30 days have passed since their previous screening. For these subjects, use of ELF or Pro-C3 results previously obtained for this study will be extended for an additional 30 days up to a total of 60 days. There are no restrictions on the number of re-screens permitted for these subjects.

Potential study subjects who previously screened and failed only ELF or only Pro-C3 but met all other inclusion criteria and met none of the exclusion criteria for this study may be re-screened.

8.3. Subject Withdrawal Criteria

8.3.1. Early Termination of Subjects from the Study

Subjects who discontinue the study should complete all scheduled safety assessments at the Early Termination Visit. If an Early Termination Visit and a scheduled visit coincide, procedures for both visits should be completed, without duplication. Subjects must discontinue the study for the following reasons:

- Subject withdraws consent;
- Subject unwilling or unable to follow study procedures, per judgment of the investigator;
- Investigator, sponsor, or Regulatory Authority judge that further dosing with study drug would be harmful to the subject;
- Subject experiences an SAE that is judged, by the investigator and the sponsor, to be related to study drug;
- Subject experiences a Grade 3 CTCAE AE judged, by the investigator and the sponsor, to be related to study drug;
- Subject experiences a Grade 4 CTCAE AE judged, by the investigator and the sponsor, regardless of the relation to study drug;
- Subject experiences a Grade 3 or Grade 4 CTCAE laboratory abnormality judged by the investigator and the sponsor, to be related to study drug except for asymptomatic elevations in cholesterol or triglycerides which are accepted;

- Subject with normal ALT and bilirubin at baseline who experiences confirmed, non-cholestatic ALT $>3 \times$ ULN and bilirubin $>2 \times$ ULN OR subjects with elevated ALT at baseline who experiences confirmed, non-cholestatic ALT $>10 \times$ baseline value and bilirubin $>2 \times$ ULN;
- Subject experiences a confirmed,
 - QTcF interval 500 msec;
OR
 - QTcF interval change from baseline ≥ 60 msec that has an absolute value ≥ 480 msec. The value of an individual ECG time point is the average of the triplicate values
 - “confirmed” is defined as the abnormality duplicated, at least 1 hour after the abnormality is first noted, by the results of a set of 3 ECGs performed in triplicate, at least 5, but not more than 10 minutes between each assessment;
- Subject experiences any hepatic AE or SAE judged by the investigator or sponsor as DILI and to be related to study drug and not to the subject’s underlying NASH.

Subjects who discontinue the study due to the safety stopping criteria will be replaced if the investigator and sponsor agree and the criteria outlined in Section 7.5 are not violated. Subjects who discontinue the study for non-safety reasons may be replaced.

If a subject is withdrawn from the study the reason(s) for withdrawal must be documented in the subject’s medical record and CRF. An Early Termination Visit should be performed. All subjects must be followed for safety until the time of the follow-up evaluation or until study drug related toxicities resolve, return to baseline or are deemed irreversible, whichever is longer.

Subjects who cannot be reached after 3 documented attempts to be contacted to schedule a follow-up visit will be considered lost to follow up.

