7.7. Safety Criteria for Adjustment or Stopping Doses

7.7.1. Individual Subject Criteria

If any of the criteria below are met by an individual subject, then no further dosing will occur at any of the study sites until a review of all available safety information is performed by the DSMB, Medical Monitor, and Sponsor. Appropriate Regulatory Agencies and Ethics Committees will be informed as applicable. If it is later determined that further dosing can be performed safely then an application for a substantial protocol amendment will be submitted to the appropriate Regulatory Agencies and Ethics Committees, if applicable. Stopping criteria for an individual subject includes:

- Grade 3 or higher CTCAE AEs possibly or probably related to study drug as determined by the investigator and sponsor;
- Grade 4 CTCAE AEs regardless of relation to study drug as determined by the investigator and sponsor;
- Any SAEs thought to be related to the study drug as determined by the investigator and sponsor.

For subjects experiencing any hepatic AEs or SAEs judged by the investigator or sponsor to be related to study drug, the investigator, DSMB, Medical Monitor and Sponsor will review all available safety data and make a determination to proceed with one of the following options:

- If the event was a drug-induced liver injury (DILI), considered as increases in aminotransferases (AT) $>3 \times$ ULN or $>3 \times$ baseline where baseline is defined as the average values of Screening and Day -1, no additional subjects will be dosed until it is determined that it is safe to proceed and in addition the frequency of blood chemistries will increase to daily, if appropriate.

- Repeat testing of ALT, AST, ALP, TBL will be performed within 48-72 hours to confirm the abnormality.
- If there are persistent elevations of AT > 3 x ULN or a 2-fold increase above baseline values (for those subjects with elevated values prior to drug exposure) upon repeat testing then close observation visits should be implemented and/or discontinuation of drug should be considered. Close Observations are described in Section 7.8.
- If the event was not a DILI, as defined above, one of the following actions will be taken:
 - Dose an entire additional cohort at the same or lower dose than the dose taken by the subject that experienced the event in question;
 - Continue to pause the study, until it is determined, that it is safe to proceed.

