11.1.6.2. Blood Chemistry

Samples will be collected before study drug dosing and after at least an 8-hour fast; however, in case of an early termination or recheck, subject fasting is not required prior to sample collection. The following tests will be performed:

- ALT
- Albumin
- ALP^a
- Amylase, total^a or pancreatic amylase
- Anion gap
- AST
- Bicarbonate
- Bilirubin (total, unconjugated, conjugated)
- Blood urea nitrogen
- Calcium
- Chloride
- Cholesterol (total, high-density lipoprotein [HDL], and low-density lipoprotein [LDL])
- Creatinine
- Creatine kinase^b
- eGFR, using CKD-EPI method
- Glucose
- HbA1c^c
- Lipase
- Phosphorus
- Potassium
- Sodium
- Triglycerides

^a Reflex fractionation, if greater than ULN

^b Reflex fractionation if greater than critical value

^c HbA1c will be collected at Screening, D28, EOS and ET

Subjects with normal ALT and bilirubin at baseline who have ALT >3 x ULN and bilirubin >2 x ULN OR subjects with elevated ALT at baseline who have ALT > 10 x baseline value and bilirubin >2 x ULN will also have serum gamma-glutamyltransferase (GGT) determined at the time these abnormalities are discovered. For these subjects, GGT may be repeated, as clinically indicated.

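### The ALT-plus-bilirubin withdrawal criterion (8.3.1) and the GGT reflex rule (11.1.6.2) have no branch for subjects with normal ALT and raised bilirubin at baseline: a minor safety gap

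*Combined protocol and SAP*

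**What the plan says.** **Withdrawal (protocol 8.3.1).** The combined criterion has two branches, and both need a confirmed, non-cholestatic rise.

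- Branch 1: "Subject with normal ALT and bilirubin at baseline who experiences confirmed" ALT >3 x ULN with bilirubin >2 x ULN.
- Branch 2: "subjects with elevated ALT at baseline who experiences confirmed, non-cholestatic ALT" >10 x baseline with bilirubin >2 x ULN. It sets no condition on baseline bilirubin.

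**GGT (protocol 11.1.6.2).** The reflex test uses the same split. It opens with "Subjects with normal ALT and bilirubin at baseline who have ALT >3 x ULN and bilirubin >2 x ULN", adds the elevated-ALT group, and says that these subjects "will also have serum gamma-glutamyltransferase (GGT) determined at the time these abnormalities are discovered". GGT is not in the scheduled chemistry panel.

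**Entry (protocol 8.2).** Exclusion 10 bars "Subjects with total serum bilirubin >1.5 x ULN, unless the subject has Gilbert's Syndrome". Gilbert's subjects above 1.5 x ULN may enter if a condition on direct bilirubin is met. Exclusion 19 covers "Safety laboratory abnormalities at Screening which are clinically significant as determined by the investigator", and exclusion 6 leaves clinically significant hepatic disease to the investigator in the same way. Neither is an automatic bar to a mildly raised bilirubin.

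**Other hepatic rules.** One part of 7.7.1 opens with "For subjects experiencing any hepatic AEs or SAEs judged by the investigator or sponsor to be related to study drug" and leads to "Repeat testing of ALT, AST, ALP, TBL will be performed within 48-72 hours to confirm the abnormality". A separate list in 7.7.1 gives criteria on which stopping is to be considered, among them ALT or AST >5 x baseline when baseline is <2 x ULN.

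**The concern.** The two branches look as if they cover everyone, but they do not. Baseline ALT and bilirubin can each be normal or raised, which gives four combinations. The branches cover three. Normal ALT with raised bilirubin is left out, and the entry criteria allow it.

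At stake is equal treatment under a mandatory stop. Of the withdrawal rules that apply to these subjects, some need a judgement that the event is related to study drug, is DILI or makes further dosing harmful. Others need a Grade 4 AE, or are only to be considered. The combined criterion is the one rule that acts on ALT and bilirubin values whatever the cause. Safety is a primary objective, and section 5.4 describes this as the first study of CRV431 in this population.

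**Working it through.** No sample size or error rate is involved. The check lists the baseline combinations, then compares thresholds. Values are multiples of ULN.

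**Step 1: which branch applies.** Inputs are the baseline conditions in 8.3.1; 11.1.6.2 gives the same result.

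| Baseline ALT | Baseline bilirubin | Branch | Required on treatment |
|---|---|---|---|
| normal | normal | 1 | ALT >3, bilirubin >2 |
| normal | raised | none | cannot be met |
| raised | normal | 2 | ALT >10 x baseline, bilirubin >2 |
| raised | raised | 2 | ALT >10 x baseline, bilirubin >2 |

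The rule was also evaluated as written at baseline ALT 0.5, 0.8 and 1.0 with baseline bilirubin 1.2, 1.5 and 2.5 (the last possible only with Gilbert's). With on-treatment bilirubin 2.5, it did not fire at ALT 4 or at ALT 20. At the same ALT baselines with baseline bilirubin 0.8, it fired at both.

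**Step 2: can the uncovered group enrol?** Exclusion 10 does not bar total bilirubin above 1.0 and up to 1.5. Exclusion 9 sets only upper limits on liver enzymes. No visible criterion requires a raised ALT. Inclusion 4 is redacted, so an ALT minimum cannot be strictly ruled out, but branch 1 itself provides for entrants with normal ALT.

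**Step 3: how far the 7.7.1 trigger fills the gap.** Assume baseline AST is also <2. The trigger is then 5 x baseline ALT, and the unreached band runs from 3.0 up to that value.

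| Baseline ALT | 5 x baseline | Band above 3.0 | Width |
|---|---|---|---|
| 0.6 | 3.0 | none | 0 |
| 0.7 | 3.5 | 3.0 to 3.5 | 0.5 |
| 0.8 | 4.0 | 3.0 to 4.0 | 1.0 |
| 0.9 | 4.5 | 3.0 to 4.5 | 1.5 |
| 1.0 | 5.0 | 3.0 to 5.0 | 2.0 |

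Below 0.6 the band is also empty. Above the band the 7.7.1 trigger applies, but it only calls for stopping to be considered, so the gap narrows there without closing.

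The AST assumption matters. Section 7.7.1 sets its tiers on ALT/AST together. If a baseline AST from 2 to below 5 puts the subject in the 3 x baseline tier, the trigger is at most 3 x 1.0 = 3.0 and the band disappears.

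**Step 4: example.** On-treatment ALT is 3.5 and bilirubin 3.0, confirmed and non-cholestatic, with AST below its own trigger and the event not Grade 4.

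- Entered at ALT 0.8, bilirubin 0.9: branch 1 applies, since 3.5 > 3 and 3.0 > 2. Withdrawal is mandatory whatever the cause.
- Entered at ALT 0.8, bilirubin 1.2: no branch applies, and 3.5 is below 5 x 0.8 = 4.0. No ALT- or bilirubin-based discontinuation trigger is met unless a relatedness or harm judgement is made.

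**Step 5: GGT.** The reflex rule omits the same group, with no upper ALT limit. No other rule orders GGT.

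**The case against.** Much of the case on the other side stands, and it is why the point is minor.

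- **Other protections remain.** Section 8.3.1 still requires withdrawal for DILI, a related SAE, a related Grade 3 event, a related Grade 3 or 4 laboratory abnormality, any Grade 4 AE, or a judgement that further dosing would be harmful. Section 7.7.2 stops dosing after one confirmed, related case with aminotransferases >3 x ULN. Section 7.7.1 also has a criterion based on symptoms with a rise in eosinophils. Section 11.3 sets a low bar for calling an event related, and investigator and sponsor know the treatment (7.3.3).
- **Close observation may not need relatedness.** Section 7.8 starts on confirmed early signs of possible DILI. Its reference to 7.7.1 leaves open whether the relatedness wording there carries over.
- **The protocol accepts a similar outcome elsewhere.** A subject entering at ALT 1.2 x ULN needs ALT above 10 x 1.2 = 12 x ULN under branch 2, so the same example event would not force withdrawal there either.
- **GGT is not the whole work-up.** ALP and bilirubin fractions are already scheduled, and 7.8 calls for biliary disease to be ruled out and for further tests as appropriate.

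None of this supplies the missing branch. The protocol gives fully normal subjects a mandatory value-based stop although the same safeguards cover them too.

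Two stronger readings are tempting. A reader might infer that these subjects have no hepatic stopping protection; the rules above show otherwise. A reader might also infer a plain drafting error, because branch 2 ignores baseline bilirubin. The documents give no reason either way, and a deliberate choice is possible: a fixed 2 x ULN limit discriminates poorly when bilirubin is already raised.

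**Conclusion.** The gap is real and minor. Subjects with normal ALT and bilirubin above ULN at baseline can enrol, and the combined withdrawal criterion and the GGT reflex cannot apply to them at any ALT. What is left uncovered for withdrawal is a confirmed, non-cholestatic rise to ALT >3 x ULN with bilirubin >2 x ULN that nobody judges related or harmful, that is not Grade 4, and that leads to no discretionary stop.

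The unreached ALT band, at most 3.0 to 5.0 x ULN, assumes baseline AST <2 x ULN. The example also assumes an event below Grade 4, because the documents do not reproduce the CTCAE cut-offs. How many Gilbert's subjects above 1.5 x ULN can enter depends on how the direct-bilirubin condition is read. The size of the affected group is not stated and is probably small; 12 + 12 = 24 of the 36 planned subjects receive CRV431. No endpoint or analysis is affected.

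**What to change.** In 8.3.1 and 11.1.6.2, delete *and bilirubin* from the baseline condition of the first branch, so that it applies to any subject with normal ALT at baseline. Keep ALT >3 x ULN and bilirubin >2 x ULN. Every baseline then falls in exactly one branch, and both branches use the bilirubin limit that branch 2 already applies whatever the baseline bilirubin.

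The cost is two words in each of two sections, by protocol amendment. ALT and bilirubin are already in the scheduled chemistry, so the only added test is an unscheduled GGT in each newly covered case.

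The downside is an occasional extra withdrawal. From a baseline bilirubin of 1.5 x ULN, a 2.0/1.5 = 1.33-fold rise reaches the limit (2.0/1.2 = 1.67-fold from 1.2), although ALT >3 x ULN is still needed. A Gilbert's subject entering above 2 x ULN, and staying there, would stop on confirmed, non-cholestatic ALT >3 x ULN alone. A separate baseline-relative bilirubin limit for Gilbert's subjects is not recommended here. It would be a new rule, and the documents do not support a threshold for it: 7.7.1 uses bilirubin >2 x baseline only when baseline ALT/AST is 5 x ULN or more.
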